#### **7.5.2.1. Image Acquisition Process**

Pictures will be taken from the patient's lesions at the visits detailed in the Schedule of Assessments Table 1.

At baseline and for inclusion criterion purposes, as per the site investigator, several pictures of the primary lesion should be taken in order for [REDACTED] to decide which image is the best quality image, to include in the database, as the primary lesion. Thereafter, all other pictures of the primary lesion should be taken in the same way (light, angle, etc.) as the baseline one so that the course of the wound can be assessed. Color reference cards with an individual barcode (unique patient identifier) which will be recorded into the CRF and optimized for automatic detection and reading should be placed next to the lesion before any image is taken.

Similar rules apply for the secondary and tertiary lesions.

All pictures will be uploaded into the database. The pictures will be linked to their corresponding visit.

#### **7.5.2.2. Image Analyses**

Lesion images will be analysed using the following methods.

1. Two reviewers will independently perform a two-step review of the lesion images:
  - a. The first step is a patient-level analysis in which the baseline and final images for each patient are de-identified with respect to order and are randomly labeled as image A or image B. Each reviewer will compare the images to assess whether image A is worse, image B is worse, or if there is no difference between images A and B. If there is discordance between the reviewers' assessments, the reviewers will discuss the case together to attempt concordance.
  - b. The second step is a review of all patient images taken as baseline and every two weeks during the 12-week trial. Each on-treatment analysis will be compared to baseline and scored as worsened, improved, or no change. The aggregated categorical scores across all patients for each time point will be correlated with the aggregate BWAT total score for each corresponding time point. If there is discordance between the reviewers' assessments, the reviewers will discuss the case together to attempt concordance.

2. The patient images will be color calibrated and analysed using JMP (a SAS product) to produce an RGB (Red Blue Green) score. The RGB scores will be used to calculate image changes over the course of each patient's study participation.

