6.5 Randomization and blinding

This was an open-label, single-arm study with no randomization. Efforts to minimize assessment bias were implemented by including an independent review of the images. A protocol for the review and scoring of the images was produced.

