6.6 Study methods

6.6.1 Bates-Jensen Wound Assessment Tool (BWAT)

The Bates-Jensen Wound Assessment Tool (BWAT) score is collected through a questionnaire of 13 items, which are evaluated individually with a score of 1 to 5. BWAT is summarized by a total score which is calculated by adding up the scores of all individual items. Therefore, the total score ranges from 13 to 65 and can be only calculated if all items are answered. However, for the purpose of this analysis missing items were imputed as described in Section 8.4. Note that the BWAT contains two extra variables to indicate the location and shape of the lesion that are not used for the calculation of the total score.

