6.6.2 Independent Image Review

Standardized lesion images were evaluated by two independent reviewers. The independent reviewers evaluated all images and assessed the evolution of the lesions compared to Week 1 by indicating if the lesion improved, worsened or did not change.

The assessment was performed in two separate steps in the following order:

1. Blinded Review: reviewers compared Week 1 to Week 12 on a blinded manner without knowing the order of the visits.
2. Unblinded Review: reviewers assessed the evolution of the lesions (primary, secondary, and tertiary) for all visits comparing them to Week 1.

For any discordant scores, the evaluators had to discuss and try to find agreement. In situations where concordance could not be reached, the worst result will be used for the analysis.

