9.2.2 Secondary endpoints

9.2.2.1 *Change from baseline in BWAT total and component scores by visit*

BWAT Score is collected at Week 1, Week 2, Week 4, Week 6, Week 8, Week 10, Week 12 and Follow-up. Differences in absolute and relative change from baseline will be also presented. Differences from baseline will be tested using a Paired Student's T-Test. (Shell T-7). Additionally, a figure presenting the evolution (mean, and 95% confidence interval) of the total score and

individual items by visit will be presented (Shell F-2). This analysis will be done using Observed Cases.

9.2.2.2 *The previous analysis will also be done for the secondary and tertiary lesions if there is enough data. Change from baseline in imaging score by visit*

Image evaluation will be summarized separately for the blinded and unblinded reviews. Percentages for each category and their exact 95% confidence interval (Clopper-Pearson) will be presented. Imputation methods will not be used for this score.

9.2.2.3 *Change from baseline in the Pain Visual Analog Scale (VAS) by visit*

Absolute change from baseline will be calculated as differences in the total score from Week 1 to Week 12. Descriptive statistics will be presented. Differences between the two visits will be analyzed using a Paired Student's T-Test. (Shell T-7)

The Week 1 to Week 12 analysis will be done using Multiple Imputation, and supported by the different sensitivity analysis as specified in Section 8.4. A forest plot summarizing these results will be produced presenting the estimated change from baseline and 95% confidence interval for the different imputation methods. These analysis will also be done for the PP population.

Additionally, the VAS Score is collected at Screening, Week 1, Week 2, Week 4, Week 6, Week 8, Week 10, Week 12 and Follow-up. VAS scores will be summarized by visit. Differences in absolute and relative change from Week 1 to each visit will be presented descriptively. Finally, differences in absolute change from Week 12 to Follow-up will be summarized. Statistically significant differences from the reference values will be tested using a Paired Student's T-Test (Shell T-7). Additionally, a figure presenting the evolution (mean, and 95% confidence interval) of the VAS score by visit will be presented (Shell F-2). This analysis will be done using Observed Cases.

9.2.2.4 *Change from baseline in total and subscales of wound QoL score by visit*

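### The planned image–BWAT correlation on all-patient visit aggregates cannot separate patient-level agreement from a shared time trend, and the SAP neither carries it forward nor lists it as dropped

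*Protocol*

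**What the plan says.** Protocol 7.5.2.2 sets out a two-step image review by two independent readers.

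- Step 1a is at patient level and blinded to order: "The first step is a patient-level analysis in which the baseline and final images for each patient are de-identified with respect to order". Neither document sets its result against BWAT.
- Step 1b is a "review of all patient images taken as baseline and every two weeks during the 12-week trial". The scale has three categories: "Each on-treatment analysis will be compared to baseline and scored as worsened, improved, or no change". The Protocol then adds: "The aggregated categorical scores across all patients for each time point will be correlated with the aggregate BWAT total score", matched by time point. It does not say how the three categories are to be aggregated or which coefficient is meant.

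SAP 6.6.2 confirms that the by-visit step is not blinded to order: "Unblinded Review: reviewers assessed the evolution of the lesions (primary, secondary, and tertiary) for all visits comparing them to Week 1". On BWAT, SAP 9.2.2.1 states: "BWAT Score is collected at Week 1, Week 2, Week 4, Week 6, Week 8, Week 10, Week 12 and Follow-up". Under Protocol 7.5.2 the site investigator scores it, and its change from Week 1 to Week 12 is the SAP primary endpoint (5.2.1).

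The SAP's own analysis of the images (9.2.2.2) is the percentage in each category with Clopper-Pearson intervals, separately for the blinded and unblinded reviews. Its correlations of BWAT are with VAS (9.2.4.2), end-of-infusion concentration (9.4.3) and PD inhibition (9.5.2). None is with images. Section 10, which summarises changes from the Protocol, does not mention the image–BWAT correlation.

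**The concern.** The unit of the planned correlation is the visit, not the patient. Averaging over patients removes most of the individual variation and leaves whatever moves with study week. Two series that both drift in one direction will then tend to correlate, whether or not the same patients are improving on both.

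The trial's setting makes a shared drift plausible without agreement. BWAT is scored by an unblinded site investigator, and the by-visit image readers know the order of the visits, so expectation alone could push both measures the same way.

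What is at stake is limited but real. In an open-label, single-arm trial, whether the images support the investigator-scored BWAT is a natural question. A high aggregate r in a report could be taken as an answer to it, and it would not be one.

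**Working it through.** **Inputs from the documents.** There are 15 patients (Protocol 9.5, SAP 6.4). Image readings every two weeks over 12 weeks give Weeks 2, 4, 6, 8, 10 and 12, so six on-treatment points; baseline cannot be scored against itself. BWAT is available at the same weeks, and "the total score ranges from 13 to 65". With complete data, the mean BWAT total differs from the mean change only by a constant, so r is the same for either. The documents state no figure for this correlation, so there is none to reproduce.

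**Assumptions not in the documents.** All SDs, trend sizes and image probabilities below.

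**Nominal limit.** For six pairs there are 4 degrees of freedom, with t = 2.776. The two-sided 5% limit is r = t/√(t² + 4) = 2.776/√(7.706 + 4) = 0.811.

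**Why aggregation matters.** With a residual SD of 4 per patient, the residual SD of a visit mean is 4/√15 = 1.03. The time trend is not reduced at all.

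**Model 1.** At visit v = 1 to 6, BWAT change = slope × v + patient effect (SD 5) + residual (SD 4). The probability that an image is read as improved is 0.1 + step × v, drawn independently of BWAT, so the measures are unrelated once visit is known. Pearson r is taken over the six pairs (mean BWAT change, proportion improved); a negative r looks like agreement. There were 20,000 runs per setting.

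| BWAT slope per visit (fall at sixth visit) | Image step | Median r | 5th to 95th percentile | Share with abs(r) > 0.811 |
|---|---|---|---|---|
| -0.7 (6 × 0.7 = 4.2) | 0.06 | -0.62 | -0.92 to 0.01 | 20% |
| -1.0 (6.0) | 0.08 | -0.75 | -0.95 to -0.30 | 36% |
| -1.5 (9.0) | 0.10 | -0.84 | -0.97 to -0.54 | 59% |

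With no trend the median is about 0 and 5% of runs pass 0.811. With small trends (slopes -0.3 and -0.5, falls of 1.8 and 3.0 points; steps 0.03 and 0.04) the medians are -0.27 and -0.44.

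**Model 2, a different structure as a check.** Patient slopes have SD 5 at Week 12, and residuals have SD 4 with autocorrelation 0.6. A three-category image score is cut from a latent course with the same mean trend. Here the image is coded so that worse is higher, and agreement is positive.

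- Measures unrelated within patients: median aggregate r is -0.01 with no trend, then 0.25, 0.61, 0.78, 0.85 and 0.88 for mean falls of 2, 4, 6, 8 and 10 points. The patient-level correlation with visit means removed is 0.00 throughout.
- Measures related (underlying patient-level correlation 0.8), 8-point fall: aggregate r is 0.91, against about 0.85 when unrelated. The visit-adjusted patient-level value is 0.60, against 0.00.
- Measures opposed (visit-adjusted patient-level r about -0.6), 8-point fall: the aggregate r is still 0.79.
- Varying the SDs (patient 3 to 8, residual 3 to 5) and the width of the no-change band: the median is 0.77 to 0.93 for an 8-point fall and 0.41 to 0.80 for a 4-point fall.
- Images reaching an early plateau while BWAT falls linearly: 0.26. A trend in BWAT only: 0.00.
- More patients do not help. With 100 patients, a 4-point fall and no patient-level agreement, the median is 0.92.

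**The case against.** Several points on the other side stand.

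- **The correlation is not bound to be strong.** It needs a sizeable trend of similar shape in both measures. With no trend, a small trend or an early plateau in one measure, r is not reliably high. In two of the three tabulated settings most runs stay inside 0.811. A reader might infer that the method always produces a strong correlation; that is not so.
- **No document gives it an inferential role.** The Protocol does not call it validation, and the trial is described as exploratory (SAP 6.4) and proof of concept (SAP 8.7).
- **The SAP's bias safeguard does not depend on it.** A reader might connect the correlation with SAP 6.5: "Efforts to minimize assessment bias were implemented by including an independent review of the images". That sentence credits the image review, which includes the order-blinded comparison of Week 1 with Week 12, analysed separately. Neither that step nor the primary test is touched.
- **It may never be run.** Protocol section 9, which the SAP is to detail, does not mention it, and SAP 9.2.2.2 analyses the images another way. Its absence from section 10 is a documentation gap, not proof that it will be reported.
- **An aggregate correlation is not empty.** It carries weak information that the group moved in one direction on both measures.

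The core of the concern remains: if the statistic is reported as the Protocol describes it, it cannot tell agreement from a shared trend.

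**Conclusion.** The point holds as a minor one. A correlation on about six all-patient aggregates can be strong with no patient-level agreement, and under a sizeable shared trend it barely separates related from unrelated measures (median 0.91 against about 0.85 at an 8-point fall). The size rests wholly on assumed SDs and trends: the median runs from about 0 to -0.84 over the settings of model 1. That the statistic cannot separate the two explanations when a trend is shared does not rest on those values.

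The effect is confined to an exploratory corroboration analysis that stands in the Protocol alone. The Protocol and SAP should be reconciled on whether it is done.

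**What to change.** State in SAP section 10 that the aggregate correlation of Protocol 7.5.2.2 is replaced by an exploratory patient-level analysis. For each patient, tabulate BWAT change from Week 1 to Week 12 for the primary lesion by the blinded image category (improved, no change, worsened). Use a tie-corrected rank measure such as Kendall's tau-b, with a permutation p-value or bootstrap interval. A single visit removes the common time trend, and the blinded step removes knowledge of order.

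If all visits are used, adjust for visit. Without that, in model 2 at an 8-point fall, the within-patient correlation of unrelated measures is still about 0.20; with visit means removed it is 0.00.

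SAP 6.5 and 6.6.2 describe the image review in the past tense. If it was already complete, label the new analysis post hoc. If the aggregate correlation is reported at all, do not present it as evidence of agreement.

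The data are already planned for collection, so the cost is a short SAP entry. Changing the Protocol text as well would follow its section 10.9, with a written amendment and approval as appropriate. The statistical price is a wide interval, with about 15 patients and heavy ties on a three-category score.

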### **7.5.3. Quality of Life - Wound QOL (HRQOL)**

The Wound-QoL questionnaire measures the disease-specific, health-related quality of life of patients with chronic wounds. It consists of 17 items on impairments which are always assessed in retrospect to the preceding seven days. The Wound-QoL is completed by the patient [52]. The Wound-QoL will be available in the specific language of each participating country for this study (English and Spanish) to ensure that each patient will understand all questions. All the information (questions/answers) will be entered into the CRF. The global score and subscale scores will be calculated programmatically in accordance with the scoring rules. The source data (paper) will be faxed / emailed to the sponsor and the original kept in the Investigator Files (TMF).

## 8. STUDY CONDUCT

### 8.1. Schedule and Time of Assessments

The Schedule of Assessments to be performed for each part of the clinical trial is described in Table 1.

The following priority order will be in effect when more than one assessment is required at a particular time-point, with PK blood sampling being performed nearest to the specified time:

1. Lesion and pain score
2. Blood samples for safety assessments
3. 12 Lead ECG
4. PK and biomarker blood sampling
5. HRQOL score (wound QOL)

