## 4. OVERALL DESIGN AND PLAN OF THE STUDY

### 4.1. Overview

[REDACTED] To reach the study objectives, 15 evaluable CUA patients who complete the 12-week treatment period will be enrolled

[REDACTED] will be responsible for the diagnosis of CUA together with the locally treating physician at the study site (team decision, two-pairs-of-eyes decision). The decision to include the patient into the study should be made based on the following criteria [48]:

- The diagnosis of calciphylaxis can be made when:
  1. The following clinical features are all present, or
  2. Two of the following clinical features and typical histopathological findings are present
- Clinical features:
  1. A patient on chronic haemodialysis or haemofiltration or haemodiafiltration for chronic kidney disease
  2. More than 2 painful and non-treatable skin ulcers with concomitant painful purpura
  3. Painful and non-treatable skin ulcers on the trunk, extremities, or penis with concomitant painful purpura
- Histopathological findings:

Skin biopsy is recommended only if the three clinical findings presented above are not present and will be left to the discretion of the treating physician. Typical histopathological findings of the skin are as follows:

  - Necrosis and ulceration of the skin with calcification of the tunica media and internal elastic membrane of small to medium-sized arterioles of dermis and subcutaneous fat
  - Concentric stenosis due to oedematous intimal thickening of the small to medium-sized arterioles of dermis and subcutaneous fat

Intense pain as primary manifestation followed and associated with cutaneous lesions and palpation of firm calcified (leather-like) subcutaneous tissue surrounding the lesion is suggestive of calciphylaxis. Typically, the lesions do not occur at sites primarily affected by venous insufficiency or arterial malperfusion. In view of the painful character of the lesions, palpation is left to the discretion of the treating physician.

The diagnosis of calciphylaxis can be supported by findings obtained from a skin biopsy. Benefits of a biopsy include exclusion of other conditions that can mimic calciphylaxis such as vasculitis. The characteristic histological features of calciphylaxis include calcification, microthrombosis, and fibrointimal hyperplasia of small dermal and subcutaneous

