### 7.5.1. Pain Score -VAS

The Visual Analogue Scale (VAS) will be used to assess pain, as per the patient. A VAS is a measurement instrument that aims to measure a characteristic or attitude that is believed to range across a continuum of values and cannot easily be directly measured. For example, the amount of pain that a patient feels ranges across a continuum from none to an extreme amount of pain.

Operationally, a VAS is usually a horizontal line, 100 mm in length, anchored by word descriptors at each end, as illustrated in

[figure not shown]

Figure 4 The patient marks on the line the point that he feels represents his perception of his current status. The VAS score is determined by measuring in millimetres from the left hand end of the line to the point that the patient marks [51].

[figure not shown]

Figure 4: VAS Analogue Scale

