#### 7.5.2. Lesion Score – Bates-Jensen Wound Assessment Tool

The site investigator will use the Bates Jensen Wound Assessment Tool (BWAT) to assess the course of the lesion. BWAT is a measuring instrument used to assess and monitor healing in pressure ulcers and other chronic wounds[49]. It is not, however, specific for CUA. It uses a numerical scale to rate wound characteristics from best to worst possible. It consists of 15 items, two of which (location and shape) are not scored. Scored items are:

- Size
- Depth
- Edges
- Undermining or pockets
- Necrotic tissue type
- Necrotic tissue amount
- Exudate type
- Exudate amount
- Surrounding skin colour
- Peripheral tissue oedema
- Peripheral tissue induration
- Granulation tissue
- Epithelialization

Each item should be scored from 1 to 5, with 1 being the best for that attribute.

Of note, elements of the Bates-Jensen Wound Assessment tool which imply probing the wound or measuring its depth are left to the discretion of the treating physician at the site and are not compulsory. The BJWAT total score will be calculated using a standard methodology for any missing values. Additionally, scores for the component items will be assessed longitudinally. Improvement or worsening will be assessed in the total score and the individual component scores.

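### The assessment order does not put the pain VAS and Wound-QoL ahead of wound examination, so visit-to-visit differences in procedure can enter two secondary endpoints

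*Protocol*

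**What the plan says.** Protocol 8.1 opens its list with "The following priority order will be in effect when more than one assessment is required at a particular time-point" and adds that PK blood is to be drawn nearest its specified time. The order is:

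1. "Lesion and pain score", as a single item
2. safety bloods
3. 12-lead ECG
4. PK and biomarker blood
5. Wound-QoL

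Images are not in the list.

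On the pain scale, Protocol 7.5.1 says: "The patient marks on the line the point that he feels represents his perception of his current status". On Wound-QoL, Protocol 7.5.3 says: "It consists of 17 items on impairments which are always assessed in retrospect to the preceding seven days". On the lesion score, Protocol 7.5.2 says: "The site investigator will use the Bates Jensen Wound Assessment Tool (BWAT) to assess the course of the lesion". The same section leaves the elements that involve probing or depth measurement to the treating physician.

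Protocol 4.2 and Table 1 place the VAS and the BWAT at the same treatment visits. Table 1 schedules Wound-QoL at Weeks 1, 6 and 12, when both of the others are also due. It labels the on-treatment ECG, electrolyte, ionised calcium and PK/PD samples as pre-dose and end of infusion, but gives the VAS and Wound-QoL no timing relative to the infusion.

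SAP 8.4 counts the VAS and Wound-QoL among the key secondary endpoints. SAP 9.2.2.3 and 9.2.2.4 analyse change from Week 1 with paired t-tests. The only measure against assessment bias in SAP 6.5 is the independent image review.

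**The concern.** A patient-reported measure is usually collected before the patient is examined or told how the disease is progressing, and in the same way at each visit. Nothing in the protocol or SAP requires this for either questionnaire.

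For the VAS the issue is examination pain. A scale that asks about the present moment can pick up pain caused by exposing or probing a wound minutes earlier. Whether it does so may depend on the site, the visit and the physician's choice about probing.

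For Wound-QoL the issue is mainly contact with the investigator. Ranked last, it can follow the wound assessment by an investigator who knows the patient is on SNF472, and at Week 1 it can follow the start of dosing.

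The trial has no control arm. A procedural difference between Week 1 and Week 12 therefore cannot be separated from change on treatment in these two endpoints.

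**Working it through.** The plan gives no figure on this point. Its only power calculation (15 patients, 60% against 25% healed or partly healed) concerns the lesion and does not depend on assessment order. The check is therefore a comparison of the texts, followed by the algebra of the change score.

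**1. VAS: what the order permits.** Item 1 of Protocol 8.1 has no internal sequence. A site that takes the VAS before uncovering the wound complies, and so does a site that takes it after scoring. One site may also do it differently at two visits. Because probing is optional (Protocol 7.5.2), the examination itself can differ between visits.

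**2. VAS: when this matters.** Let examination add a mean of *a* mm to the VAS at Week 1 and *b* mm at Week 12, averaged over all patients and counting zero for those who mark the scale first.

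Observed mean change = (true Week 12 + *b*) − (true Week 1 + *a*) = true change + (*b* − *a*)

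- VAS always first: *a* = *b* = 0, so there is no bias.
- VAS always after an equally painful examination: *a* = *b*, so the effect cancels.
- Order or probing differs between the visits: *b* − *a* need not be zero.

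**3. Illustration; every input is an assumption.** Suppose examination adds *d* = 10 to 30 mm, and in a net share *p* = 10% to 50% of patients it precedes the VAS at one of the two visits only. The shift is *p* × *d* in absolute size:

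- 0.10 × 10 = 1 mm
- 0.25 × 20 = 5 mm
- 0.50 × 30 = 15 mm

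If the exposed visit is Week 1, the shift is −1 to −15 mm and looks like pain relief. If it is Week 12, the shift is +1 to +15 mm and looks like worsening. With *p* = 0 it is zero. The range is thus −15 to +15 mm, and the documents do not locate the trial within it.

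**4. The same illustration in the VAS responder categories (SAP 9.7.2).** Take true pain of 40 mm at both visits and *d* = 20.

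- Examined first at Week 1 only: −100 × (40 − 60)/60 = 33%, which falls in the category of at least 30% reduction.
- Examined first at Week 12 only: −100 × (60 − 40)/40 = −50%, which counts as worsening.

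Neither patient's underlying pain has changed.

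**5. Baseline fallback.** SAP 8.8 replaces a missing Week 1 value with the Screening value. Table 1 schedules the VAS at Screening but no BWAT, although a lesion overview and images are due. For such a patient, baseline and Week 12 come from visits with different wound procedures.

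**6. Wound-QoL.** A seven-day recall gives little weight to one examination that day, so examination pain is a weak route. Two others remain. First, item 5 ranks below lesion scoring, so the questionnaire can follow the investigator's assessment and any remark made about the wound. Second, item 4 covers PK samples taken before dosing and at the end of infusion on Week 1 Day 1, and Wound-QoL is not tied to the earlier one. SAP 8.8 defines baseline as the Week 1 Day 1 value and sets no pre-dose condition for the questionnaire. Completion after the first infusion has started is therefore allowed, though not required.

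**The case against.** The strongest reply is that Protocol 8.1 sets priorities and not a clock sequence, and that a site can follow it while taking the VAS first and completing Wound-QoL after the pre-dose sample but before dosing. That is correct. The gap is missing specification, not a mandated wrong order. A reader might infer that Wound-QoL always follows examination, scoring and photography; the text does not say so, and images are not in the list.

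A reader might also infer that examination pain affects both questionnaires alike. The seven-day recall in Protocol 7.5.3 argues against this, and also limits what a first infusion of a few hours could do to the Week 1 Wound-QoL.

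A third tempting inference is that the bias favours SNF472, because healing wounds would be probed less at Week 12. No text supports that. Protocol 4.1 does say "In view of the painful character of the lesions, palpation is left to the discretion of the treating physician", but that sentence concerns diagnosis. If the same caution governed BWAT probing, examination would be gentlest when pain is worst, plausibly at Week 1, and the bias would run against the drug.

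Finally, patients know that they receive SNF472, can see their own lesions and attend up to 36 treatment sessions. No passage says that investigators report scores to patients. Reordering one visit leaves that general expectation effect in place.

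All of this stands and limits the point. It does not supply the missing instruction: nothing in the documents puts the patient's own report first or keeps its position constant across visits.

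**Conclusion.** The point holds as a specification gap in two secondary endpoints. For the VAS, order and probing can differ between Week 1 and Week 12, and any resulting difference in examination pain passes directly into the mean change. For Wound-QoL, the order permits completion after the open-label wound assessment and, at Week 1, after dosing has begun; examination pain is a minor route.

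Size and direction cannot be determined from the documents. The −15 to +15 mm range rests wholly on assumed values of *d* and *p*. It shows how a shift would arise and is not an estimate. If examination pain is constant across visits, the bias is zero.

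The BWAT primary endpoint does not depend on patient report and is not affected. The case for acting is that the change is free, not that a large bias has been shown.

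**What to change.** Replace the list in Protocol 8.1 with the following order, applied identically at every visit where the items are due:

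1. Pain VAS and Wound-QoL (where scheduled), completed by the patient before dressing removal, lesion scoring, images, any discussion of the wound and the start of the infusion.
2. Lesion score and images.
3. Safety bloods, ECG, then PK and biomarker samples as now, with PK still nearest its specified time.

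Record the completion time of both questionnaires so that adherence can be checked.

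The cost is a rewording of one short list and a time entry on the form. No assessment, visit or staff is added, and PK timing is unchanged. The change does not remove the expectation bias of an open-label, single-arm trial, and the report should not claim that it does.

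If data have already been collected, the sponsor should establish from the sites what order was used, including whether Week 1 questionnaires preceded the infusion, and report it as a limitation of the VAS and Wound-QoL results. Patients whose VAS baseline came from Screening should be identified in that account.
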